Machine learning (ML) methods have been extraordinarily effective at integrating many clinical patient variables into one holistic risk prediction tailored to each patient. We have conducted a pilot study to assess the feasibility of predicting surgical outcomes after surgery for UIAs in a small single-center sample. We found that prediction was feasible with good performance metrics, and also identified the most important factors to be included in such models. To the authors' best knowledge, a robust, multicenter, externally validated prediction model or predictive score for surgical outcome after microsurgery for UIAs does not yet exist.

Accurate preoperative identification of patients at high risk for adverse outcomes would be clinically advantageous, as it would allow enhanced resource preparation, better surgical decision-making, enhanced patient education and informed consent, and potentially even modification of certain modifiable risk factors. The aim of the *Prediction of adverse events after microsurgery for intracranial unruptured aneurysms* (PRAEMIUM) study is therefore to develop and externally validate a clinically applicable, robust ML-based prediction tool based on multicenter data from a range of international centers.

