### Authorship

Each center must contribute data from at least 100 patients to be included. Each eligible institution designates 1 primary author per center who will be included in the primary author list. Each eligible center may also designate 2 additional secondary authors, who will be included in the author list as part of the PRAEMIUM study group, and who

will be fully indexed in PubMed as contributing authors. The sponsor institution is entitled to 3 primary authors and to 4 secondary authors.

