### Data Collection

Each center will collect their data either retrospectively, or from a prospective registry, or from a prospective registry supplemented by retrospectively collected variables. Data from patients operated from January 1st 2010 and onwards will be eligible for inclusion. **Data collection should be completed, and anonymized data should be sent to the sponsor institution ([[contact]](mailto:[contact])) by 1st of August 2021.**

A standardized Excel spreadsheet will be provided by the sponsor. The data will be entered in standardized and anonymized form. This spreadsheet will only contain a study-specific patient number. The data set is anonymized source data that includes clinical data extracted from electronic health records (retrospectively or from a prospective registry of already existing data). The data will be anonymized upon entering them into the PRAEMIUM Excel spreadsheet, after which the patients will be numbered consecutively and there will be no way to trace the data back to individual patients. No identifiable data such as date of birth will be included. Whenever the PRAEMIUM Excel spreadsheet is transferred, it will be encrypted using a password and sent through a secure institutional e-mail server to **[contact]**. The password will be sent in a separate e-mail. Some missing data is acceptable, but should be kept to a minimum (i.e. must be < 10%)

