### Sample Size

While even the largest cohort with millions of patients is not guaranteed to result in a robust clinical prediction model if no relevant input variables are included (“garbage in, garbage out” – do not expect to predict the future from age, gender, and body mass index), the relationship among predictive performance and sample size is certainly directly proportional, especially for some data-hungry ML algorithms. To ensure generalizability of the clinical prediction model, the sample size should be both representative enough of the patient population, and should take the complexity of the algorithm into account. For instance, a deep neural network – as an example of a highly complex model – will often require thousands of patients to converge, while a logistic regression model may achieve stable results with only a few hundreds of patients. In addition, the number of input variables plays a role. Roughly, it can be said that a bare minimum of 10 positive cases are required per included input variable to model the relationships. Often, erratic behavior of the models and high variance in performance among splits is observed when sample sizes are smaller than calculated with this rule of thumb. Of central importance is also the proportion of patients who experience the outcome. For very rare events, a much larger total sample size is consequentially needed. For instance, a prediction based on 10 input features for an outcome occurring in only 10% of cases would require at least 1000 patients including at least 100 who experienced the outcome, according to the above rule of thumb. In general and from personal experience, we do not recommend developing ML models on cohorts with less than 100 positive cases and reasonably more cases in total, regardless of the rarity of the outcome. Also, one might consider the available literature on risk factors for the outcome of interest: If epidemiological studies find only weak associations with the outcome, it is likely that one will require more patients to arrive at a model with good predictive performance, as opposed to an outcome which has several highly associated risk factors, which may be easier to predict. Larger sample sizes also allow for more generous evaluation through a larger amount of patient data dedicated to training or validation, and usually results in better calibration measures.

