For this study, based on our expertise and on the rules of thumb mentioned above, we estimate that a minimum of 250 patients with positive outcome are required to extract generalizable features. With an incidence of these outcomes of

around 10% that means that a minimum of 2500 patients are required for training. For adequate evaluation of calibration at external validation, we estimate that – as a bare minimum – another 1500 patients (thus, approximately 150 with positive outcomes) will be required. Thus, in total, we estimate that **4000 patients** are necessary to arrive at a robust model. More data will likely lead to greater performance and better calibration.

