### Predictive Modeling

A KNN imputer will be co-trained to impute any missing data that may occur in future application of the model. If there is missing data in the training set, it will be imputed using said KNN imputer. Features or patients with a missingness greater than 25% will be excluded. Data will be standardized and one-hot-encoded. In case of major class imbalance – which is expected for the abovementioned endpoint – random upsampling or synthetic minority oversampling (SMOTE) will be applied to the training set. All features will initially be provided to the model for training. If necessary, we will apply recursive feature elimination (RFE) to select input features on the training data.

We will trial the following algorithms for binary classification: Generalized linear model (GLM), generalized additive model (GAM), stochastic gradient boosting machine (GBM), naïve Bayes classifier, artificial neural network, support vector machine (SVM), and random forest. Each model will be fully trained and hyperparameter tuned where applicable. The final model will be selected based upon AUC, sensitivity, and specificity, as well as calibration metrics on the resampled training performance. Training will occur in repeated 5-fold cross-validation with 10 repeats.

The one final model will then be assessed on the external validation data only once. 95% confidence intervals for external validation metrics will be derived using the bootstrap.

The threshold for binary classification will be identified on the training data alone using the AUC-based “closest-to-(0,1)-criterion” or Youden’s index to optimize both sensitivity and specificity. All analyses will be carried out in R Version 3.6.2.

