### Evaluation

The performance of classification models can roughly be judged along two dimensions: Model discrimination and calibration. The term *discrimination* denotes the ability of a prediction model to correctly classify whether a certain patient is going to or is not going to experience a certain outcome. Thus, discrimination describes the accuracy of a binary prediction – yes or no. *Calibration*, however, describes the degree to which a model’s predicted probabilities (ranging from 0% to 100%) correspond to the actually observed incidence of the binary endpoint (true posterior). Many publications do not report calibration metrics, although these are of central importance, as a well-calibrated predicted probability (e.g. your predicted probability of experiencing a complication is 18%) is often much more valuable to clinicians – and patients! – than a binary prediction (e.g. you are likely not going to experience a complication).

Resampled training performance as well as performance on the external validation set will be assessed for discrimination and calibration. In terms of discrimination, we will evaluate AUC, accuracy, sensitivity, specificity, positive predictive value (PPV), negative predictive value (NPV), and F1 Score. In terms of calibration, we will assess the Brier score, expected-observed (E/O)-ratio, calibration slope and intercept, the Hosmer-Lemeshow goodness-of-fit test, as well as visual inspection of calibration plots for both datasets, which will also be included in the publication.

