### **Expected Results**

We expect to arrive at a generalizable model based on multicenter international data that is likely to predict the abovementioned binary outcomes consistently with an AUC of at least 0.70 (more realistically 0.8 or greater) and that is well-calibrated. A web-based prediction tool will also be created for each of the two models using the *shiny* environment, much akin to e.g. <https://neurosurgery.shinyapps.io/impairment>. This web-based app will be available for free on any internet-capable device (mobile or desktop), and should be stable on most devices due to the server-based computing. The costs for maintaining the server will be carried by the sponsor.

The collected data will be stored by the sponsor for 10 years. The large dataset will be open to further analysis and will be provided to any of the contributing centers at reasonable request and after approval by all other centers. The goal is to enable other analyses using the collected dataset. If any additional analyses lead to publication, all contributors will be included as co-authors and all co-authors will have the opportunity to review said manuscript beforehand. Any contributing study center has the right to veto publication of any subsequent analyses that includes their data.

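### The external-validation intervals make no allowance for centre; in the ordinary reading, those for E/O and calibration intercept describe the sampled centres and are too narrow to support the generalisability aim

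*Combined protocol and SAP*

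**What the plan says.** The only statement on interval estimation is in Predictive Modeling: "95% confidence intervals for external validation metrics will be derived using the bootstrap". It gives no resampling unit, interval type or number of resamples. No section mentions a centre effect, centre-specific performance, a measure of heterogeneity, or whether whole centres are reserved for validation.

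The data are clustered by design. The Introduction sets the aim to "develop and externally validate a clinically applicable, robust ML-based prediction tool based on multicenter data from a range of international centers". Under Authorship, "Each center must contribute data from at least 100 patients to be included". Data Collection allows different sources: "Each center will collect their data either retrospectively, or from a prospective registry, or from a prospective registry supplemented by retrospectively collected variables". All centres do use one standardized spreadsheet.

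Generalisability and calibration are the declared goals. Sample Size opens one argument with "To ensure generalizability of the clinical prediction model, the sample size should be both representative enough of the patient population" and sizes the 1500 validation patients on calibration grounds ("For adequate evaluation of calibration at external validation, we estimate that"). Evaluation lists "expected-observed (E/O)-ratio, calibration slope and intercept" among the measures. Expected Results states "We expect to arrive at a generalizable model based on multicenter international data", expects it to be well calibrated, and announces a free web tool.

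**The concern.** E/O and calibration intercept show whether predicted risks are right on average. If centres differ in outcome rate after the input features are accounted for, these two measures shift directly from centre to centre. A bootstrap that resamples patients from the pooled set treats the centres at hand as fixed. Its width reflects the number of patients and events, and hardly responds to how far the centres differ.

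The web tool is meant for patients in other hospitals. An interval that omits between-centre spread could let it be presented as well calibrated elsewhere with more certainty than the data give. The plan also has no step that would estimate the spread.

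**Working it through.** **Inputs from the documents.** Validation set N = 1500; incidence about 10%, so about 150 events (Sample Size); at least 100 patients per centre (Authorship).

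**Inputs assumed.** Between-centre SD of the log-odds after case-mix adjustment (τ) of 0.1, 0.2, 0.3 or 0.5; 15, 10 or 5 validation centres; normally distributed centre effects; discrimination of about AUC 0.75. At τ = 0.1, 0.2, 0.3 and 0.5, most centres around a 10% risk would lie at about 8-12%, 7-14%, 6-17% and 4-23%.

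**The plan's own figures.** 250/0.10 = 2500; 1500 × 0.10 = 150; 2500 + 1500 = 4000. All reproduce. The plan states no target interval width, so there is none to reproduce.

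**Patient-level precision.** SE[ln(E/O)] = √((1 − p)/events) = √(0.9/150) = 0.0775. With a true E/O of 1, the 95% interval is exp(±1.96 × 0.0775) = 0.86 to 1.16.

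**Adding centres.** Let M = Σmᵢ²/N be the size-weighted mean number of patients per centre. To first order,

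true SE / patient-level SE = √(1 + c·τ²·M),

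where c is the mean of p(1 − p). If every patient had 10% risk, c = 0.09. With risks spread to give an AUC near 0.75, c is about 0.082. If whole centres are held out, 1500/100 = 15 is the largest possible number of centres, with M = 100:

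| τ | c = 0.082 | c = 0.09 |
|---|---|---|
| 0.1 | √1.082 = 1.04 | √1.09 = 1.04 |
| 0.2 | √1.328 = 1.15 | √1.36 = 1.17 |
| 0.3 | √1.738 = 1.32 | √1.81 = 1.35 |
| 0.5 | √3.05 = 1.75 | √3.25 = 1.80 |

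At τ = 0.3 and a ratio of 1.35, the interval that allows for centre is exp(±1.96 × 0.0775 × 1.35) = 0.81 to 1.23, against 0.86 to 1.16. With 5 centres of 300 and c = 0.09, the ratio at τ = 0.3 is √(1 + 0.09 × 0.09 × 300) = √3.43 = 1.85.

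If centres are split between training and validation, M falls. For 40 centres with 1500/40 = 37.5 validation patients each, the ratio is only 1.02 (τ = 0.1) to 1.36 (τ = 0.5).

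**Simulated coverage.** The table shows nominal 95% patient-level bootstrap intervals for E/O, judged against the value for the wider population of centres (1500 patients in equal-sized whole centres, ranges over separate simulations):

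| τ | 15 centres | 10 centres | 5 centres |
|---|---|---|---|
| 0 | 94-95% | 94-96% | 93-95% |
| 0.1 | 92-94% | 93-94% | 90-92% |
| 0.2 | 90-91% | 88-89% | 80-85% |
| 0.3 | 84-87% | 79-83% | 70-75% |
| 0.5 | 70-76% | 63-67% | 49-54% |

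Monte Carlo error is about 1-2 points. One run of 500 sets gave 90% for 15 centres at τ = 0.3, above the range shown; the normal approximation at a ratio of 1.35 gives about 85-86%. The calibration intercept behaves like E/O: at τ = 0.3, 91%, 82% and 72% with 15, 10 and 5 centres.

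**Does the alternative work?** A random-effects summary of the centre intercepts with a Hartung-Knapp interval covered about 93-97% in these settings. A percentile bootstrap of whole centres covered only 80-86% for E/O with 5 centres.

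**The case against.** The strongest reply is that the plan contains no stated error. It does not say that patients are the resampling unit, a patient-level interval is valid for the centres sampled, and no passage ties the word well-calibrated to an interval or threshold. The calibration statement stands under Expected Results and is an expectation. Calibration will also be judged from several measures and plots together. All of this stands: the gap is one of specification and scope, and it does harm only if the interval is read as covering other centres. But reaching other centres is the study's declared purpose, and the plan offers no other analysis for it.

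It is also fair that the size rests on assumptions. Differing data sources make residual centre differences plausible but do not show them, and the common spreadsheet works against them. At τ = 0.1 with 10 or 15 centres there is practically nothing to correct. An unknown SD is, however, a reason to estimate it.

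A reader might infer that the SE ratios above are a guaranteed minimum. The documents do not support that. The ratios depend on c, on τ, and on holding out whole centres, which external validation ordinarily suggests but no section states.

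**Conclusion.** The concern holds in this form: read in the ordinary way, the planned intervals for E/O and calibration intercept apply to the sampled centres and are too narrow to support a statement about centres in general. At about 100 patients per centre the SE is understated by a factor of approximately 1.04, 1.15-1.17, 1.32-1.35 and 1.75-1.80 at assumed SDs of 0.1, 0.2, 0.3 and 0.5. The factor is larger with fewer, bigger centres, smaller if centres are split, and 1 if there is no heterogeneity.

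A reader might go further and infer that the bootstrap intervals are invalid, that the total of 4000 is wrong, or that the point estimates are biased. None of these follows. The intervals are valid for the centres sampled, the sample-size arithmetic reproduces, and the issue concerns only what the intervals can support. Nor is any claim made here about AUC intervals.

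This should be changed before the validation data are analysed. Confidence is medium, because the between-centre SD and the number of validation centres are not in the documents.

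**What to change.** - State that external validation uses whole centres that contributed nothing to training, and carry a centre code into the pooled file. Data Collection describes a spreadsheet with only a study-specific patient number. Provenance should nevertheless be recoverable, since each centre sends its own file and the veto right in Expected Results presupposes knowing whose data are whose.
- Keep the bootstrap, name patients as the resampling unit, and label its intervals as applying to the sampled centres.
- Add a random-effects summary of the centre-specific calibration intercept (and E/O) with a Hartung-Knapp interval, and report the between-centre SD. Base any generalisability statement on this summary.
- If centres have few events, use a one-stage random-intercept logistic model with the logit of predicted risk as offset. A centre of 100 at 10% risk has only about 10 events, and the two-stage summary fell to 89-91% coverage with 15 centres of 100 at 5% risk.
- A prediction interval for a new centre is optional and must be labelled approximate (81-89% coverage in simulation with 15 centres).

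No new patients or clinical variables are needed. The cost is a centre column, a short addition to the plan, a little more analysis and wider intervals. With 15 centres, the mean width for the calibration intercept rises from 0.35 to 0.39 at SD 0.1, and from 0.35 to 0.50 at SD 0.3.

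### All classification measures are read at one cut-off that is not tied to clinical consequences, and no net-benefit analysis is planned

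*Combined protocol and SAP*

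**What the plan says.** In the combined protocol and SAP:

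- **Predictive Modeling.** "The threshold for binary classification will be identified on the training data alone", by the closest-to-(0,1) criterion or Youden's "index to optimize both sensitivity and specificity". The choice between the two rules is left open. Sensitivity and specificity also enter the selection of the final algorithm. Random upsampling or SMOTE is planned for major class imbalance, which is expected. No recalibration step follows.
- **Evaluation.** For discrimination, "we will evaluate AUC, accuracy, sensitivity, specificity, positive predictive value (PPV), negative predictive value (NPV), and F1 Score". Of these seven, all but AUC need the cut-off. The section adds a calibration set that does not need it: Brier score, E/O ratio, slope, intercept, Hosmer-Lemeshow test and plots. It says that a well-calibrated probability "is often much more valuable to clinicians" than a yes/no call.
- **Introduction.** Among the expected advantages of identifying high-risk patients before surgery are "better surgical decision-making, enhanced patient education and informed consent".
- **Sample Size.** One incidence of about 10% serves all three endpoints.

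The document contains no clinically chosen risk threshold, no net-benefit measure and no comparison with flagging everyone or no one.

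**The concern.** Maximising sensitivity plus specificity looks neutral, but it fixes an exchange rate between missed events and false alarms, and that rate comes from how common the event is. The three endpoints differ in gravity: under Endpoint Definitions they run from any deviation from Clavien-Dindo grade 0 to an mRS above 2. Two endpoints with the same incidence would nevertheless receive the same weight under Youden, and the rarer of two endpoints would receive the larger weight whatever its severity.

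What is at stake is how the published results can be read. Discrimination and calibration describe the predictions. They do not say at which risk thresholds acting on the predictions is better than a policy that needs no model. A tool offered for surgical decisions and consent invites that question, and the planned output does not answer it.

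**Working it through.** **The plan's own figure.** 250 / 0.10 = 2500 for training; 1500 × 0.10 = 150 events for validation; 2500 + 1500 = 4000. This reproduces and confirms 10% as the planning incidence *p*. Nothing below changes it.

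**Weight implied by Youden.** Let C_FN and C_FP be the costs of a missed event and a false alarm. Expected loss per patient is p(1 − Se)C_FN + (1 − p)(1 − Sp)C_FP. Maximising Se + Sp is the same as minimising (1 − Se) + (1 − Sp), so it is the right choice only when p·C_FN = (1 − p)·C_FP, that is, C_FN / C_FP = (1 − p)/p.

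- p = 10% (Sample Size): 0.90/0.10 = 9
- p = 5% (assumed): 0.95/0.05 = 19
- p = 20% (assumed): 0.80/0.20 = 4

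For a calibrated model the matching risk cut-off is 1/(1 + 9) = 0.10, the incidence itself.

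**Closest-to-(0,1).** At its optimum the ROC slope is (1 − Sp)/(1 − Se), so the implied ratio is [(1 − p)/p] × (1 − Se)/(1 − Sp). With a binormal ROC of equal variances this is again 9. If the case SD is 1.5 times the control SD (assumed) and AUC is 0.70, then Se = 0.606 and Sp = 0.706, giving 9 × 0.394/0.294 ≈ 12. ROC shape therefore matters as well as incidence.

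**What would be reported.** Assumptions: calibrated model, normal linear predictor, p = 10%. AUC 0.70 and 0.80 are from Expected Results; 0.75 lies between. Per 1000 patients, TP = 100·Se and FP = 900·(1 − Sp), computed before rounding.

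| AUC | Se | Sp | TP | FP | Flagged | PPV | Accuracy |
|---|---|---|---|---|---|---|---|
| 0.70 | 0.646 | 0.643 | 64.6 | 321.4 | 39% | 17% | 64% |
| 0.75 | 0.687 | 0.680 | 68.7 | 288.0 | 36% | 19% | 68% |
| 0.80 | 0.730 | 0.719 | 73.0 | 253.3 | 33% | 22% | 72% |

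The Youden cut-off falls at risk 0.100 in each row. Calling every patient negative gives accuracy 900/1000 = 90%.

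**Net benefit.** NB = TP − FP × t/(1 − t) per 1000, where t is the risk at which a user would act. The documents give no t; the values below are assumed for illustration only. Flag-none is 0 throughout.

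| AUC | t | Youden rule | Flag all | Model risk cut at t |
|---|---|---|---|---|
| 0.70 | 5% | 64.6 − 321.4/19 = +48 | 100 − 900/19 = +53 | +57 |
| 0.70 | 20% | 64.6 − 321.4/4 = −16 | 100 − 900/4 = −125 | +7 |
| 0.80 | 20% | 73.0 − 253.3/4 = +10 | −125 | +23 |
| 0.80 | 25% | 73.0 − 253.3/3 = −11 | 100 − 900/3 = −200 | +17 |

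At AUC 0.70 the fixed rule loses to flag-all at 5% and to flag-none at 20%, while the same model's probabilities beat both.

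**Effect of resampling.** With 1:1 upsampling (ratio assumed) and no recalibration, the odds are multiplied by 9. A true risk of 10% becomes (1/9 × 9 = 1) 50%. A true risk of 18%, the example value in Evaluation, becomes 0.18/0.82 × 9 = 1.98, or about 66%. A decision curve on such probabilities would be read at the wrong thresholds.

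**The case against.** The strongest defence is that the plan does not rest on the cut-off. Evaluation gives calibration central importance and ranks a probability above a binary call, and the only numerical performance target in Expected Results is an AUC. That stands. A reader might infer that the only measures of practical use are those read at the cut-off; the calibration set contradicts this.

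A reader might also infer that the study fails an objective of proving better decisions. The Introduction's stated aim is to develop and externally validate a tool, and better decision-making appears there as an expected advantage. The gap is between intended use and evaluation.

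Nor do the documents support saying that the classification figures will mislead. PPV and NPV are planned, with bootstrap intervals for external validation, and a PPV near 20% itself shows that about four in five flagged patients have no event. From PPV and 1 − NPV a careful reader could even work out the thresholds between which the fixed rule beats flag-none and flag-all: about 6% to 17% at AUC 0.70, and 4% to 22% at AUC 0.80. That covers one cut-off, not the probabilities used at other thresholds.

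Finally, Expected Results does not say that the web tool will return a yes/no class, so that should not be assumed.

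**Conclusion.** The point holds in this form: six of the seven discrimination measures depend on a single cut-off chosen without reference to clinical consequences, and no planned analysis compares use of the predictions with flagging all or no patients.

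The 9:1 weight is exact for Youden at 10% incidence. It will differ for each endpoint with that endpoint's own incidence, and under closest-to-(0,1) it also depends on ROC shape. The weight does not depend on calibration. The risk cut-off of 0.10 does, and the PPV and accuracy ranges were computed under the calibrated-model assumptions given above. The net-benefit figures rest in addition on assumed thresholds.

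No planned estimate is invalidated, and the sample size is unaffected. This is a low-cost improvement that would let the validation address the use for which the tool is offered.

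**What to change.** 1. Before the external data are opened, have the clinical investigators state, for each endpoint, the range of risk thresholds relevant to decisions.
2. If upsampling or SMOTE is used, recalibrate the probabilities to the original incidence using training data only, before the single external assessment.
3. On the external data, report net benefit over the stated range as a decision curve, against flag-all and flag-none, with intervals from the bootstrap already planned.
4. Name one cut-off rule in advance. Keep the cut-off-based measures as secondary description, and show accuracy beside the always-negative rule.

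The cost is a short addition to the SAP, a recalibration step where resampling is used, and one further analysis of the external predictions. No new patients or variables are needed. The downsides are that a threshold range must be agreed and that the tool may show little net benefit. The result would show potential utility only. Because Inclusion and Exclusion Criteria admit operated patients alone, it could not show improved decisions or inform the choice between surgery and observation.
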